- Suitability to Have a Dog Checklist: A home assessment checklist to assess suitability of the home environment for dog placement. The checklist documents availability of space for dog to play, availability of space for toileting of dog, the presence of other pets in the home, and cleanliness and safety of the home. The measure was developed specifically for this study because no other such measure exists.

- **Screening Phase**

1. Preliminary Screening:

- Prior to scheduling a potential participant for a clinic qualifying visit the potential participant's chart notes will be examined to determine whether there are indications that the potential participant is ineligible for the study and whether he/she has ongoing mental health treatment at VA.
- A telephone screening will be completed to assess eligibility and thoroughly explain the study procedures.
- A referral letter from mental health provider will be obtained, or confirmation that a signed referral letter will be available by clinic qualifying visit will be obtained.
- In order to help manage expectations, potential participants should be informed that the screening phase is an ongoing process and that final eligibility will not be determined until the successful completion of the dog Placement or Pairing process.

If any CPRS note, the telephone screen, or other information indicates a potential participant is ineligible, the LSI or a designated member of the study team will inform the individual that they cannot participate in the study.

2. Activities prior to Clinic Qualifying Visit.

- If a signed referral checklist has not been received from a mental health provider in advance of the scheduled Clinic Qualifying visit, a member of the study team must confirm by telephone prior to the visit that the potential participant will be bringing it in person to the appointment. If confirmation is not received, the Clinic Qualifying visit must be rescheduled.

- A member of the study team will make a reminder call to the potential participant. If applicable, the potential participant will be reminded to bring the signed referral checklist to the appointment.

3. Clinic Qualifying Visit at VA study site.

- Informed consent and HIPAA authorization will be obtained.
- If not already received, the referral checklist/letter will be collected.
- The Demographic interview and CAPS will be completed
- The C-SSRS will be administered using the ‘during the last month’ time frame.

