9. WPAI:GHP
10. Medication Log
11. Dog Knowledge Test

Additional visit-related activities and information:

- Participants will receive \$25.00 for this home visit.
- Secondary contact information (full name, phone number(s), address, and relationship to the participant): if contact information has already been collected verify accuracy of the information provided by the participant. If not already collected obtain the information or remind the participant to provide the information prior to the pairing process.
- If children between the ages of 5 and 10 years reside in the home provide the AVMA family education form.

The Home Clearing Visit: will take place at participant's home. This visit is conducted to confirm that the participant's home remains suitable for a dog. At the Home Clearing visit the following will occur:

- The Suitability to Have a Dog Checklist will be re-administered.
- Review of the DOG course and, if the participant did not pass the Dog Knowledge test (score $\geq 80\%$), provide further education to ensure the participant is aware of the responsibilities and obligations of dog ownership.
- Veterinary Checklist packet can be provided at this visit or at the week 1 post pairing visit. This decision will be based on the discretion of the local study team.
- Collect or verify secondary contact information (full name, phone number(s), address, and relationship to the participant).
- Once a study dog trainer considers the participant has sufficient knowledge and the home is confirmed to be suitable for a dog, the participant will be unblinded to the type of dog (SERV vs. EMOT) to which they were randomized and will be provided with vendor contact information.
- Review study requirements and expectations that follow the completion of the Home Clearing visit and pairing process.

If randomized to the Service Dog group, the vendor will contact the participant to coordinate travel. It should be explained to participants that:

- They will travel to the vendor's location for training to become a service dog handler.
- Training can last several weeks, though in most cases it will last between 1-2 weeks.

- The pairing process will cover basic obedience commands, execution of the specific trained tasks, basic dog care, and the public access rights given Service Dogs by the ADA. The participant can request an overview of the training class and ask questions as needed.

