- Travel to and from the vendor's facility may be completed by air or personal vehicle.
- Reimbursement for use of a personal vehicle will at the government mileage rate paid on return from training.
- To avoid out-of-pocket expenses, the vendor will pay for air travel (and will later be reimbursed by VA).
- Out-of-pocket expenses may be unavoidable in some circumstances. In this instance, participants will be reimbursed by VA for expenses allowed by Federal Travel Regulations in a timely manner.
- The vendor will provide accommodation during the training session.
- The vendor will provide food or reimburse food expenses during the training.
- ADA Service Dog Public Access Rights pocket card.

Expenses for accommodations are included as part of the Statement of Work (SOW) for the Vendor contract. Vendors will provide food or reimburse food expenses for participants while they are at the Service Dog pairing visit, using the government per diem rate for that locale. The vendor will invoice the VA for the expense as dictated by the contract SOW.

If randomized to the Emotional Support Dog group, the participant will work with local dog trainer to receive their dog and dog training. It should be explained to participants that:

- The local dog trainer will train the participant how to handle his/her dog
- The training will take place in the participant's home and local vicinity
- The training will last between 1 and 2 days.
- Additional training visits can be scheduled as needed.
- On completion of training, the dog trainer will provide the participant with a list of important phone numbers (probably printed on a refrigerator magnet).
- An emotional support dog ID card, with the name and picture of the assigned dog, and a brief summary of the dog's right under US law on the back of the card.
- If applicable a letter signed by the LSI establishing the right of an emotional support dog to live in housing where pets are not allowed.
- If applicable a letter signed by the LSI establishing the right of an emotional support dog to fly in the cabin with the participant for commercial air travel.

IX. TREATMENT REGIMENS

For this section, the following terms are defined:

- **Participant:** A Veteran who has been enrolled in the study.

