Service Dogs (SERV). A Service Dog must be well behaved at all times and promptly respond to commands (verbal or hand signals) given by the handler. To be effective in the trained tasks, a Service Dog must exhibit a strong desire to please the handler and remain at the handler’s side, unless otherwise directed. They must be well socialized to people and other animals. Per the contract in place with the vendors, as part of Service Dogs must pass the AKC Canine Good Citizen (CGC) examination, Assistance Dogs International (ADI) Public Access Test (PAT), and also demonstrate the 5 tasks specified by the contract (Lights, Sweep, Bring, Block, and Behind).

Emotional Support Dogs (EMOT). Emotional support dogs must also be well behaved at all times, and well socialized to people and other animals. However, they are not taught specific tasks that address disabilities associated with PTSD. Emotional Support Dogs must pass the AKC Canine Good Citizen and AKC Community Canine examinations during the proofing process.

Once an Emotional Support Dog is proofed against contract standards, it will be shipped to the designated VA study site by the vendor, then kenneled until arrangements can be made by the local study coordinator or designee to place the dog with a participant.

In contrast to the 1-2 week pairing process for Service Dogs conducted at a contract vendor's property, a participant randomized to receive an Emotional Support Dog will undergo a 1-2 day "placement" process at their home, conducted by a VA Dog Trainer. As part of the placement process, handlers will be reminded about the definition of an Emotional Support Dog, the allowances regarding reasonable accommodation for housing, and provided necessary letters if required. The handler will also be shown and then be asked to demonstrate obedience commands taught to the dog. The VA Dog Trainer will also go over care of the dog and make sure the house is ready for the dog.

- **Contract Training Requirements for All Dogs**

During the proofing process, the National VA Dog Trainer, a Local VA Dog Trainer, a VA Veterinarian, or another VA employee serving on the proofing team will fill all roles specified in the testing process. Note that the proofing process will always be conducted at a vendor's property.

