 - Participants will be provided an ID card from the dog wellness/insurance contractor to take to their veterinarian so that the veterinarian may bill the insurance contractor directly. If the veterinarian's office does not want to bill the contractor, the veterinarian can call the 1-800 number provided on the card and get paid via a credit card that day by the contractor. There should be no out-of-pocket cost for participants unless they request services not covered by the insurance. The list of covered services will be provided to the participants by the insurance vendor. On rare occasion VA may need to reimburse a participant for a legitimate expense not covered by the insurance.

X. FOLLOW-UP ASSESSMENTS

- **Pairing Dates:**

The official pairing date for participants paired with Service Dogs is the date they depart from the vendor's facility after training. This should be the same date identified on their training completion certificate provided by the designated vendor.

The official pairing date for participants placed with an Emotional Support Dog is the last day of training with the VA dog trainer (Local or National Dog Trainer).

Post Pairing Monitoring Visits

- **Week 1 post-pairing visit:**

Approximately one week after receipt of the dog, the dog trainer will conduct a home visit at which the Post-Pairing Evaluation, the Veteran and Service/Emotional Support Dog Visit Report and the Dog Related Questions will be completed. If there is a child living in the home who is aged between 5 and 10 years, the dog trainer will evaluate the behavior of the dog when the child is present preferably through direct observation. If this is not possible (child at school, or elsewhere) the participant will be thoroughly interviewed instead. The participant will be provided with a Post-Pairing Survey and postage-paid envelope to complete and mail to a member of the study team. The Veterinary Checklist packet (includes form 23) will be provided to the participant. If the packet was given during the Home Clearing Visit a reminder will be provided for the return of the form or if available will be collected at the time of the visit. Provide the participant with a visit timeline calendar. Participants will receive \$10 for their time and effort.

- **Week 2 post-pairing contact: Home visit or telephone call**

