6. Any indication that a dog is being mistreated in the home environment by any member of the household.
7. Repeated refusal by the participant to go to routine veterinary visits, or decisions not to seek veterinary treatment for dog injuries or significant illnesses.
8. Diagnosis of chronic illness, hip or elbow dysplasia, or a genetic condition refractory to treatment that will likely reduce the working life of a Service Dog or the ability of an Emotional Support Dog to be a potentially positive factor on the participant.

- **Adverse Event Follow-Up**

For each reported AE, site investigators follow up with participants until the event resolves and ensure that appropriate care is provided, but there is no case report form to fill for AE follow-up.

Adverse events must be reported as Serious Adverse Events (SAE) if they meet the SAE reporting requirements described below.

- **Serious Adverse Events**

1. Definition of Serious Adverse Event (SAE)

Serious adverse events are defined by the ICH for Clinical Safety Data Management and CSP Global SOP 3.6.2, as any untoward medical occurrence that:

- Results in death,
- Is life threatening,
- Requires inpatient hospitalization or prolongation of existing hospitalization,
- Results in persistent or significant disability or incapacity,
- Is a congenital anomaly/birth defect, or
- Any other condition that, based upon medical judgment, may jeopardize the subject and require medical, surgical, behavioral, social or other intervention to prevent such an outcome.

Any adverse event that meets the definition of “Serious” will be reported on an SAE Form. All SAEs will be classified as either “related,” “possibly related,” or “not related” to study intervention. A definite causal relationship does not need to be established.

2. Serious Adverse Event Monitoring

Participants will be monitored for SAEs at each study visit and during any contact with the participant. Each serious adverse event is reported on an SAE Form. Active monitoring for SAEs begins at the time the Informed Consent Form is signed and continues until the earlier of the 30 days after the participant’s completion, early termination of study participation, or the end of the study. The final SAE monitoring review can be completed by a chart review. The date study participation ends is entered on the Study Completion/Termination Form. Safety data from the pre-randomization and post-pairing periods will be analyzed separately.

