### Per-Protocol Population (PP)

This population includes all participants who are paired with a dog.

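### The Protocol's pairing date falls after 1-2 weeks with the dog in one arm and 1-2 days in the other, and conflicts with SAP 6.4; per-protocol membership and the dog-exposed safety period need one arm-neutral start

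*Protocol*

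**What the plan says.** **Pairing date.** Protocol X (Pairing Dates) gives one rule per arm. For Service Dogs: "The official pairing date for participants paired with Service Dogs is the date they depart from the" vendor's facility once training is over. For Emotional Support Dogs: "The official pairing date for participants placed with an Emotional Support Dog is the last day of training with the VA dog trainer".

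**Length of training.** Protocol VIII (Home Clearing Visit) says of Service Dogs: "Training can last several weeks, though in most cases it will last between 1-2 weeks". Of Emotional Support Dogs it says: "The training will last between 1 and 2 days". Protocol IX repeats the contrast ("In contrast to the 1-2 week pairing process for Service Dogs conducted at a contract" vendor's property, against 1-2 days at home).

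**SAP dates.** SAP 6.4 counts months of treatment from a Service Dog pairing date that it equates with the start of training, and from receipt of the dog in the other arm.

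**What depends on pairing.** SAP 5.2 defines the per-protocol (PP) set: "This population includes all participants who are paired with a dog". Protocol XVIII (Statistical Methods) analyses all outcomes on both the intention-to-treat (ITT) and PP sets. Protocol XIII (Serious Adverse Event Monitoring) says: "Safety data from the pre-randomization and post-pairing periods will be analyzed separately". Protocol XII has separate procedures for terminations before and after pairing. Protocol VII (Preliminary Screening) adds that "final eligibility will not be determined until the successful completion of the dog Placement or Pairing process".

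**The concern.** The same calendar rule, the end of training, means a different amount of dog contact in each arm. Take a Veteran who gives up on day 5 with the dog. In the Service Dog arm training is still under way, so under Protocol X there is no pairing date and the case fits a pre-pairing termination. In the Emotional Support Dog arm training ended on day 1 or 2, so the Veteran is paired, belongs to the PP set, and any withdrawal is a post-pairing termination.

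This interval comes after randomization and after the Veteran has learned the dog type, so dropping out of it may depend on the assigned arm. PP membership would then be conditional on getting through a run-in whose length differs by arm. Dog-related events in that run-in also have no place in the Protocol's two safety periods. At stake are the comparability of the PP arms and fair counts of early failures and dog-related harms by arm.

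**Working it through.** **1. The plan's own figure, used here only as a denominator.** Inputs from Protocol Table 6 and the Sample Size text: MCS mean 33.2, SD 10.6, difference 15% (0.15 × 33.2 = 4.98), two-sided alpha 0.05, power 0.85. n = 2 × (1.960 + 1.036)² × (10.6/4.98)² ≈ 81.4, so 82 per group. Allowing for 25% loss, 82/0.75 = 109.3, so 110 per group. Both figures reproduce and are not in dispute.

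**2. Dog contact before the Protocol pairing date.** Service Dogs: 1-2 weeks = 7-14 days, longer if training runs to several weeks. Emotional Support Dogs: 1-2 days.

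- Smallest ratio 7/2 = 3.5; largest 14/1 = 14.
- Smallest gap 7 − 2 = 5 days; largest 14 − 1 = 13 days.

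**3. The conflicting dates side by side.**

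| | Protocol X | SAP 6.4 |
|---|---|---|
| Service Dog | departure from vendor, after training | start of training |
| Emotional Support Dog | last training day | receipt of dog |

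Under SAP 6.4 both arms start at about first contact. Under Protocol X they do not.

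**4. Illustration with assumed rates.** The documents give no early failure rate. Assume the same constant failure hazard in both arms, a 28-day cumulative failure q of 2%, 5% or 10%, and 110 Veterans per arm starting training. Hazard h = −ln(1 − q)/28. Failures before the pairing date = 110 × (1 − exp(−h × days)). Failures from then to day 28 = 110 × q minus that number. For q = 10% and 14 days: h = 0.1054/28 = 0.00376; 110 × (1 − exp(−0.0527)) = 5.64; 11 − 5.64 = 5.36.

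| q | Service Dog, before (7 / 14 days) | Emotional Support Dog, before (1 / 2 days) | Service Dog, after | Emotional Support Dog, after |
|---|---|---|---|---|
| 2% | 0.55 / 1.11 | 0.08 / 0.16 | 1.65 / 1.09 | 2.12 / 2.04 |
| 5% | 1.40 / 2.79 | 0.20 / 0.40 | 4.10 / 2.71 | 5.30 / 5.10 |
| 10% | 2.86 / 5.64 | 0.41 / 0.82 | 8.14 / 5.36 | 10.59 / 10.18 |

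Under these assumptions 25-51% of the 28-day Service Dog failures fall before the pairing date, against 4-7% in the other arm. At the extreme (q = 10%, 14 days against 1 day), equal true hazards would appear as 5.4 against 10.6 post-pairing failures. This shows direction and mechanism only; it is not a forecast.

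**The case against.** Much can be said for the plan, and most of it stands.

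- **SAP 6.4 already uses near-equivalent starts**, and Protocol IX defines pairing as the training process itself. SAP 5.2 says the rules for assigning population status will be documented before final analysis. No passage ties PP membership to the Protocol X date. That link is an inference, though a reasonable one, since Protocol X alone names an official pairing date.
- **Nothing leaves the trial.** ITT is everyone randomized, the Safety population is everyone consented, adverse events are collected from consent, and SAP 8 tabulates them by arm without restriction to post-pairing time. The gap concerns PP membership and the Protocol's period split. One reservation remains: outcome visits are timed from receipt of the dog, so the documents do not assure follow-up scores for a Veteran who fails in vendor training, even within ITT.
- **Timing.** Protocol XI expects bonding failures mostly within about two weeks of the Veteran getting home, which for Service Dogs is after the pairing date. That makes the lower figures above more plausible for bonding. It says nothing about bites, refusals or failed training.

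A reader might infer more than the documents support:

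- **That a bite or a dog exchange in training removes the Veteran from the paired set.** It does not. A Veteran who still completes training gets a pairing date.
- **That events disappear in one arm only.** Both arms have a pre-pairing gap; its length differs.
- **That resizing favours Service Dogs.** SAP 3.8 uses a single post-pairing termination rate for the whole study, so no arm contrast enters.
- **That a shift in outcome scores can be worked out.** The first post-pairing outcome visit is at month 3, and SAP 5.3 keeps post-replacement data out of the primary analysis. An early Emotional Support Dog failure who withdraws contributes no post-pairing score, and one whose dog is replaced contributes none to the primary analysis.

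**Conclusion.** The point holds in a limited form. Protocol X and SAP 6.4 give different starting dates and must be reconciled. If the Protocol date governs, Veterans who quit or fail in training can be left out of the PP set and handled as pre-pairing terminations, and dog-related events in training belong to neither named safety period. Both gaps exist in each arm but cover 7-14 days or more for Service Dogs against 1-2 days, a ratio of about 3.5 to 14.

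The ratio rests only on the stated training lengths. The consequence for PP rests on the inferred link between the official date and membership. The number of Veterans or events affected is unknown: the 2-10% range above is assumed, as are the constant and equal hazards. Any effect on PP outcome scores is probably small and cannot be computed from the documents. The clearer risk is an arm-dependent undercount of early failures and dog-related events wherever results are reported from pairing onward.

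**What to change.** - Reconcile Protocol X (Pairing Dates) with SAP 6.4.
- In SAP 5.2, and in the safety text of Protocol XIII and SAP 8, start PP membership and the dog-exposed safety period at the first day with the assigned dog: the first vendor training day for Service Dogs, the day the dog is received for Emotional Support Dogs. SAP 6.4 already needs both dates.
- Keep the Protocol X date for scheduling visits only.
- Report by arm the adverse events, training failures and dog exchanges between first dog contact and the Protocol X date.
- Ask Veterans who start but do not finish training to continue outcome follow-up, and state the date from which their visits are timed.

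The cost is minor wording and tabulation work, follow-up visits for any such Veterans, and a reported failure rate that may look slightly less favourable. The sample size does not change.
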